6 DISCONTINUATION

6.1 Discontinuation of Individual Subject(s) From Study Treatment

A discontinuation from treatment is a subject who enrolled in the study and for whom both study treatments are permanently discontinued for any reason. If one treatment is discontinued due to toxicity, the subject may continue on the other as monotherapy until discontinuation criteria is met. The reason for discontinuation from study treatment must be documented in the subject's medical records.

All subjects who discontinue study treatment will remain in the study and must continue to be followed for protocol specific follow-up procedures as outlined in [Table 1 Schedule of Assessments]. The only exception to this is when the subject specifically withdraws consent for any further contact with him/her or persons previously authorized by the participant to provide this information.

All participants who discontinue study treatment are to be followed for up to 3 years after their EOT, death or the final analysis, whichever occurs first per [Table 1 Schedule of Assessments].

The subject is free to withdraw from the study treatment and/or study for any reason and at any time without giving reason for doing so and without penalty or prejudice. The investigator is also free to discontinue the subject from study treatment or to terminate a subject's involvement in the study at any time if the subject's clinical condition warrants it.

If a subject is discontinued from the study with an ongoing AE or an unresolved laboratory result that is significantly outside of the reference range, the investigator will attempt to provide follow-up until the condition stabilizes or no longer is clinically significant.

Subjects who meet any of the following criteria during the study will be withdrawn from study treatment:

- Subject declines further study participation (i.e., withdrawal of consent).
- Subject is non-compliant with protocol based on the investigator or medical monitor assessment.
- Subject is found to have significantly deviated from any one of the inclusion or exclusion criteria after enrollment (subjects having clinical benefit and no DLT may be kept in the study after discussion with the medical monitor).
- Subject develops an unacceptable study drug-related toxicity (DLT) or SAE requiring discontinuation of treatment.

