- Site personnel have temporarily relocated the conduct of the study to a location that place a burden on the participant with respect to time and travel

- Participant(s) have temporarily relocated from the current study site to an alternate study site to avoid placing a burden on the participant with respect to travel
- Participant(s) have temporarily relocated from their home location and the new distances from the site would cause undue burden with respect to time and travel
- Participant has risk factors for which traveling to the site poses an additional risk to the participant's health and safety

Adherence to the original protocol as reflected in the Schedule of Assessment [Table 1] is expected, where plausible, in the case of a crisis. The alternate measures as noted in [Table 8] below are only permissible in the event of a crisis, and after discussing the need with the Astellas medical monitor or designee to implement the alternate measures. This is to allow for continuity of receiving study drug and maintaining critical safety and efficacy assessments for patients participating in the study at a time of crisis.

If one or more of the alternate measures noted below is implemented for a participant, the site should document in the participant's source document the justification for implementing the alternate measure and the actual alternate measures that were implemented, along with the corresponding time point(s).

All other assessments should be completed as outlined in [Table 1].

Table 8 Alternative Schedule of Assessments in Response to a Crisis

Critical Assessments	Alternate Approach(es)	Critical Time points						Follow-up	
		C1D1	C1D8	C1D1	Subsequent Cycles D1	Subsequent Cycles D15	EOT	30-Day Follow-up	Long-term Follow-up
General Study Procedures									
Weight	Can be obtained at local clinic	X			X				
Physical Examination	Since atezolizumab needs to be given every 2 weeks in the clinic, this will be captured in the clinic. In the event the visit is missed, this can be captured during the telehealth visit.	X	X	X	X	X	X		
Vital Signs	Since atezolizumab needs to be given every 2 weeks in the clinic, this will be captured in the clinic. In the event the visit is missed, information may be captured during telehealth visits if a patient has adequate monitoring instruments and knowledgeable and able to obtain measurements	X	X	X	X	X	X		

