Blood Sample for FLT3 and AXL	This is an exploratory endpoint. There are no alternative approaches for this assessment. If the 24 post-dose sample is not feasible, it is okay.	X							
Blood Sample for Immune Cell Immunophenotyping	In general biomarker samples are collected on atezolizumab treatment days and do not require a unique visit to the study site. These samples cannot be stored. If samples cannot be received by central lab then they should not be collected	X		X	X		X		
Blood Sample for Blast Cell Immunophenotyping	In general biomarker samples are collected on atezolizumab treatment days and do not require a unique visit to the study site. These samples cannot be stored. If samples cannot be received by central lab then they should not be collected	X		X	X		X		
PGx (whole blood and buccal swab)	This samples are collected on an atezolizumab treatment day. If the samples can be collected but the central lab cannot receive samples, samples can be stored at sites until shipping is accepted again	X							

Table continued on next page

Critical Assessments	Alternate Approach(es)	Critical Time points						Follow-up	
		C1D1	C1D8	C1D1	Subsequent Cycles D1	Subsequent Cycles D15	EOT	30-Day Follow-up	Long-term Follow-up
Pregnancy Test for WOCBP	Since atezolizumab needs to be given every 2 weeks in the clinic, this will be obtained in the clinic. In the event the visit is missed, or the patient cannot come to the clinic, the collection of samples at local facility is acceptable if the results can be made available to investigative site.	X			X		X		
Treatment									
Gilteritinib Dosing at the Clinic	Patient will be taken off study and the patient can take commercially available gilteritinib off study or receive other alternative therapies for R/R AML albeit the options are limited and not very effective. Delivery from site to patient if the patient is just on gilteritinib monotherapy is also possible.	X	X	X	X	X			
Atezolizumab Dosing at the Clinic	All atezolizumab dose needs to be administered in the clinic at every 2 week intervals. The protocol allows for patients to continue treatment with gilteritinib alone if the patient had issues related to tolerability of other clinical considerations related to atezolizumab.	X		X	X	X			
Tissue Collection									

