Bone Marrow Biopsy and/or Aspiration for disease assessment and MRD	Bone marrow assessment to be performed in the clinic. In the event this is not possible, bone marrow biopsy performed in a local facility is acceptable if results can be made available to investigative site.				X		X		
Diary									
Subject Diary for Gilteritinib	Diary can be shipped directly to the patient. Accountability can be performed during the telehealth visit.	X			X				

AE: adverse event; AML: acute myeloid leukemia; AXL; a receptor tyrosine kinase encoded by the AXL gene; C: cycle; D: day; ECG: electrocardiogram; ECOG: Eastern Cooperative Oncology Group; EOT: end of treatment; FLT3: FMS-like tyrosine kinase 3; MRD: minimal residual disease; PGx: pharmacogenomics; R/R: relapsed or refractory; SAE: serious adverse event; WOCBP: women of childbearing potential.

INVESTIGATIONAL PRODUCT SUPPLY

If any of the conditions outlined above in the Participants Procedures Assessment are met, one or all of the following mitigating strategies will be employed, as needed, to ensure continuity of study supply to the participants:

- Increase stock of study drug on site to reduce number of shipments required, if site space will allow
- Use of locally available atezolizumab brands
- Direct-to-Participant shipments of study drug from the site to the participant's home (ASP2215 only)

DATA COLLECTION REQUIREMENTS

Additional data may be collected in order to indicate how participation in the study may have been affected by a crisis and to accommodate data collection resulting from alternate measures implemented to manage the conduct of the study and participant safety.

- Critical assessments for safety and efficacy based on study endpoints to be identified as missing or altered (performed virtually, at alternative locations, out of window, or other modifications) due to the crisis

13 ATTACHMENT 1: NONSUBSTANTIAL AMENDMENT 3

I. The purpose of this amendment is:

Nonsubstantial Changes	
1. Update Key Sponsor Personnel	
DESCRIPTION OF CHANGE:	Contact details for clinical research contact are revised.
RATIONALE:	Contact details of sponsor personnel are updated based on changes to study personnel.
2. Update Recommended Dose Modifications for Adverse Reactions	

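### The crisis table takes subjects off study when gilteritinib cannot be dosed at the clinic, which contradicts the Section 6.1 follow-up rule and may cost response and survival data for a logistic reason

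*Protocol*

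**What the plan says.** Protocol Appendix 12.10, Table 8, row on in-clinic gilteritinib doses: "Patient will be taken off study and the patient can take commercially available gilteritinib off study or receive other alternative therapies for R/R AML". The same cell adds: "Delivery from site to patient if the patient is just on gilteritinib monotherapy is also possible".

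Protocol Section 6.1: "All subjects who discontinue study treatment will remain in the study and must continue to be followed for protocol specific follow-up procedures". It continues: "The only exception to this is when the subject specifically withdraws consent for any further contact". The criteria in that section for leaving long-term follow-up are withdrawn consent, loss to follow-up, more than 3 years since the EOT visit, and death. A crisis is not among them. Section 5.3.3.1 collects survival status and later antileukemic treatment for all subjects.

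Appendix 12.10 gives the aim of the alternate measures: "This is to allow for continuity of receiving study drug and maintaining critical safety and efficacy assessments". Its supply section lists, for gilteritinib only, "Direct-to-Participant shipments of study drug from the site" to the participant's home, with no limit to monotherapy.

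SAP Section 7.11.4 lists or flags Covid-19-affected assessments, discontinuations and deaths. It specifies no analysis for them.

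**The concern.** The trigger for this row is logistic: closed sites, travel limits, relocation, or risk in travelling. The row nevertheless uses a term that normally describes leaving the trial, and the protocol does not say whether it means off study treatment or out of follow-up. Under the second reading, a subject could go on taking gilteritinib commercially while the trial stops recording that subject's response, remission status and survival.

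At stake are the EOT marrow (or a cycle 2 or 3 day 1 marrow that is due), the 30-day contact, and long-term remission and survival status. These feed CRc, the primary efficacy endpoint, and also event-free survival (EFS), duration of remission and overall survival (OS).

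**Working it through.** **Step 1: passages side by side.**

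| Question | Table 8, gilteritinib row | Elsewhere in the protocol |
|---|---|---|
| Status after stopping | Off study, undefined | Remains in study, one consent exception (6.1) |
| Survival data | Not addressed in the row | All subjects (5.3.3.1) |
| Home delivery of gilteritinib | Only if on gilteritinib alone | Not limited to monotherapy (12.10 supply section) |
| Missed clinic visit | Off study | Other Table 8 rows: telehealth, local laboratory, local ECG, local marrow |

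The gilteritinib row is also marked at cycle 1 day 8, when Table 1 schedules no atezolizumab infusion.

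**Step 2: how a lost assessment would enter each endpoint.**
- CRc: SAP 6.1.4 counts missing response as non-response and keeps it in the denominator. It states this for CR (with CRp, CRi, CRh and PR defined similarly) and for best response. It has no separate CRc rate entry, so non-response is the probable treatment, not a stated one.
- EFS: censored at the last relapse-free assessment. For a subject never in remission, the two treatment-failure dating rules require discontinuation because of treatment failure, so neither clearly covers a crisis departure.
- Duration of remission: censored at the last relapse-free assessment.
- OS: censored at last contact.

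**Step 3: reproduce the design.** Inputs from protocol Section 7.1 are: stop if 11 or fewer of 22 have CRc; reject if 32 or more of 49 do; null rate 50%; alternative 70%. With *p* the probability that a subject is counted as CRc,

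P(reject) = Σ over x = 12 to 22 of C(22,x) pˣ(1−p)²²⁻ˣ × P[Bin(27,p) ≥ 32 − x].

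At p = 0.70 this gives 0.802, which matches the stated 80%. At p = 0.50 it gives 0.0216, within the stated 0.025.

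**Step 4: assumed worst case.** Let a fraction *m* of subjects lose their end-of-cycle-2 response at random, and count all of them as without CRc, so p = 0.70 × (1 − m). The documents give no value for *m*.

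| m | p | Power | Chance of stage 1 stop |
|---|---|---|---|
| 0 | 0.700 | 0.802 | 0.039 |
| 2% | 0.686 | 0.737 | 0.053 |
| 5% | 0.665 | 0.625 | 0.081 |
| 10% | 0.630 | 0.423 | 0.149 |

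Of 49 subjects, 5% is about 2.5 and 10% about 5. With fixed counts, losing one subject gives power 0.736 if in stage 1 or 0.745 if in stage 2. Losing one in each stage gives 0.670.

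With null p = 0.50 × (1 − m), type I error falls to 0.0089 at 5% loss and 0.0032 at 10%. The bias in CRc is therefore downward.

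**Step 5: soften the worst case.** Suppose, as an assumption, that half of the affected would-be responders already had CRc documented. Then 10% loss gives p = 0.70 × (1 − 0.10 × 0.5) = 0.665 and power 0.625. If the 49 evaluable subjects in Section 7.1 are reached by replacing those lost, nominal power stays at 0.802, but the evaluable set is then a selected one.

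**The case against.** A reader might infer that follow-up ends and the data are lost. The documents do not say so. No passage stops follow-up for these subjects. Appendix 12.10 leaves assessments outside Table 8 as in Table 1, which includes the survival row. Table 8 marks adverse-event assessment through long-term follow-up and accepts a local marrow, including at EOT. Read with Section 6.1, off study could mean off study treatment. This stands, and it limits the point to data that may be lost.

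A reader might also take Table 8 as a site's only instruction. It is not. The supply section offers shipment, Section 5.1.3.1 allows interruption after cycle 1 for logistic reasons with return within 14 days unless otherwise discussed with the medical monitor, and alternate measures require discussion with the medical monitor first. Commercial gilteritinib is an option in the row, not a required switch.

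Three further limits stand:
- A cycle 2 day 1 or EOT marrow may already document CRc, and only departures in the first two cycles can affect the primary count. The power figures are therefore an upper bound on harm for a given loss, and they describe missing responses in general.
- Table 1 schedules no marrow after EOT for anyone, so relapse marrows after EOT are not what this wording puts at risk.
- Informative censoring is possible, because a participant's own health risk is one of the triggers listed before Table 8, but the documents do not establish it.

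None of this removes the conflict in wording. That off study can be read either way is itself the defect.

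**Conclusion.** The contradiction is real and in current text. Table 8 takes the subject off study, while Section 6.1 keeps the subject in follow-up and recognises no crisis exception. The row also conflicts with the appendix's stated aim and, on delivery, with its supply section. A site that follows the row literally could end follow-up for a non-clinical reason, and SAP 7.11.4 would only list the case.

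The size cannot be fixed from the documents. The fall in power from 0.802 to 0.625 at 5% loss and 0.423 at 10% rests on three assumptions: true CRc of 70%, random loss, and every affected subject counted as without CRc. The documents do not support the stronger statement that the outcomes are necessarily lost. Correction is worthwhile because the wording change is small and protects CRc, EFS and OS.

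**What to change.** State in the Table 8 gilteritinib row that a subject who leaves study treatment under it remains in the study for follow-up per Section 6.1, unless consent for further contact is withdrawn. Say that the already scheduled EOT marrow (local if needed), the 30-day contact and the 3-monthly telephone follow-up continue. Say also that commercial gilteritinib is recorded as subsequent antileukemic treatment with its start date.

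Reconcile the row's restriction of home delivery to gilteritinib monotherapy with the unrestricted shipment in the supply section. The sponsor decides which applies. Nothing here bears on whether treatment stops or which treatment a subject receives.

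The cost is a short protocol amendment. It adds no procedure: the EOT marrow, the local-marrow option, the telephone contacts and the collection of subsequent treatment already exist in Table 1, Table 8 and Section 5.3.3.1.

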5.3.2 Response Assessments

WAS:

Response to treatment will be defined per modified Cheson criteria [Cheson et al, 2003] as outlined below.

IS AMENDED TO:

Response to treatment will be defined per modified Cheson criteria [Cheson et al, 2003] as outlined below **for up to the end of 2 cycles and end of treatment.**

IV Synopsis and 5 Treatments and Evaluation

5.3.2.5 Complete Remission with Partial Hematologic Recovery (CRh)

WAS:

For subjects classified as being in CR, except if their ANC is $> 0.5 \text{ Gi/L}$ and their platelets are $> 50 \text{ Gi/L}$.

IS AMENDED TO:

For subjects classified as being in CR, except if their ANC is $> 0.5 \times \text{Gi}10^9/\text{L}$ and their platelets are $> 50 \times \text{Gi}10^9/\text{L}$.

IV Synopsis and 5 Treatments and Evaluation

5.3.2.9 Best Response

WAS:

Two best responses, up to the time of 2 cycles of treatment period and the EOT Visit will be defined.

IS AMENDED TO:

Two best responses, up to the time of 2 cycles of treatment period and the EOT Visit will be defined.

7 Statistical Methodology

7.2.4 Pharmacokinetics Analysis Set (PKAS)

WAS:

The pharmacokinetics analysis set (PKAS) consists of the administered population for which sufficient plasma concentration data is available to facilitate derivation of at least one pharmacokinetic parameter and for whom the time of dosing on the day of sampling is known.

IS AMENDED TO:

The pharmacokinetics analysis set (PKAS) consists of the administered population for which sufficient plasma concentration data is available to facilitate derivation of at least one pharmacokinetic parameter and for whom **at least 1 plasma concentration datum is available and both the date and time of dosing on the day of pharmacokinetic sampling and the date and time of sampling are known** ~~the time of dosing on the day of sampling is known.~~

12 Appendices

12.7 Adverse Events of Special Interest (AESI) for Atezolizumab

WAS:

- Severe cutaneous reactions (e.g., Stevens-Johnson syndrome, dermatitis bullous, toxic

epidermal necrolysis)
IS AMENDED TO:

Severe cutaneous reactions are a known risk (e.g., Stevens-Johnson syndrome, dermatitis bullous, toxic epidermal necrolysis)

12 Appendices
ADDED:
12.10 Clinical Study Continuity
INTRODUCTION
The purpose of this appendix is to provide acceptable alternate methods to assess safety and efficacy parameters, as appropriate, in the event the clinical study is interrupted at the country, state, site or participant level during any crisis (e.g., natural disaster, pandemic).
BENEFIT-RISK RATIONALE
Maintaining the safety of clinical study participants and delivering continuity of care in the clinical study setting is paramount during any crisis. The site is expected to follow the protocol and associated Schedule of Assessments [Table 1] unless the site principal investigator discusses the need with the Astellas medical monitor to implement the alternate measures.
The approach outlined within this appendix defines which assessments are required to maintain a favorable benefit/risk to the participant, to maintain overall study integrity and to provide acceptable alternate methods to complete the study required assessments and procedures if study activities are unable to be performed as described in Section 5 due to a crisis.
INFORMED CONSENT
Participants who need to follow any or all of the alternate measures outlined in this Appendix will be required to provide informed consent, which explicitly informs them of the nature of and rationale for these changes, and gain their agreement to continue participation in the study prior to the implementation of any of these changes. In the event the urgency of implementing the alternate measures does not allow for the participant to provide written consent prior to implementation, the principal investigator or designee will obtain oral agreement from the subject followed by written documentation as soon as is feasible. A separate addendum to the study informed consent will be provided to document the participant’s consent of the changes.
PARTICIPANT PROCEDURES ASSESSMENT
Sites with participants who are currently enrolled into this clinical study may consider implementing the alternate methods outlined below if one or more of the following conditions are met due to the crisis:

- **Regional or local travel has been restricted, inclusive of mandatory shelter in place measures, which makes participant travel to/from the study site nearly impossible**
- **Site facilities have been closed for clinical study conduct**
- **Site has been restricted to treating patients with conditions outside of the scope of the study**
- **Site personnel have temporarily relocated the conduct of the study to a location that place a burden on the participant with respect to time and travel**
- **Participant(s) have temporarily relocated from the current study site to an alternate study site to avoid placing a burden on the participant with respect to travel**
- **Participant(s) have temporarily relocated from their home location and the new distances from the site would cause undue burden with respect to time and travel**
- **Participant has risk factors for which traveling to the site poses an additional risk to the participant's health and safety**

Adherence to the original protocol as reflected in the Schedule of Assessment [Table 1] is expected, where plausible, in the case of a crisis. The alternate measures as noted in [Table 8] below are only permissible in the event of a crisis, and after discussing the need with the Astellas medical monitor or designee to implement the alternate measures. This is to allow for continuity of receiving study drug and maintaining critical safety and efficacy assessments for patients participating in the study at a time of crisis.

If one or more of the alternate measures noted below is implemented for a participant, the site should document in the participant's source document the justification for implementing the alternate measure and the actual alternate measures that were implemented, along with the corresponding time point(s).

All other assessments should be completed as outlined in [Table 1].

12 Appendices

ADDED:

Table 8 Alternative Schedule of Assessments in Response to a Crisis

Critical Assessments	Alternate Approach(es)	Critical Time points						Follow-up	
		C1D1	C1D8	C1D1	Subsequent Cycles D1	Subsequent Cycles D15	EOT	30-Day Follow-up	Long-term Follow-up
General Study Procedures									
Weight	Can be obtained at local clinic	X			X				
Physical Examination	Since atezolizumab needs to be given every 2 weeks in the clinic, this will be captured in the clinic. In the event the visit is missed, this can be captured during the telehealth visit.	X	X	X	X	X	X		
Vital Signs	Since atezolizumab needs to be given every 2 weeks in the clinic, this will be captured in the clinic. In the event the visit is missed, information may be captured during telehealth visits if a patient has adequate monitoring instruments and knowledgeable and able to obtain measurements	X	X	X	X	X	X		
ECOG Performance Status	Since atezolizumab needs to be given every 2 weeks in the clinic, this will be captured in the clinic. In the event the visit is missed, information can be captured during telehealth visits.	X		X	X	X	X		
AE/SAE Assessment	Since atezolizumab needs to be given every 2 weeks in the clinic, this will be obtained in the clinic. In the event the visit is missed or the patient cannot come to the clinic, telehealth visits will be allowed for non-dosing visits. Please refer to protocol schedule of assessments.	X	X	X	X	X	X	X	X
Prior and Concomitant Medications	Since atezolizumab needs to be given every 2 weeks in the clinic, this will be obtained in the clinic. In the event the visit is missed or the patient cannot come to the clinic, telehealth visits will be allowed for non-dosing visits. Please refer to protocol schedule of assessments.	X	X	X	X	X	X	X	
Electrocardiograms									

12-lead ECG	Since atezolizumab needs to be given every 2 weeks in the clinic, this will be obtained in the clinic. In the event the visit is missed or cannot be made, ECG in triplicates performed in local facility is acceptable if results can be made available to investigative site.	X	X	X	X	X	X		
Blood and Urine Collection									
Clinical Laboratory Tests (chemistry, hematology, coagulation, urinalysis)	Since atezolizumab needs to be given every 2 weeks in the clinic, this will be obtained in the clinic. In the event the visit is missed, or the patient cannot come to the clinic, the collection of samples at local facility is acceptable if the results can be made available to investigative site.	X	X	X	X	X	X		
Thyroid Function Test	Since atezolizumab needs to be given every 2 weeks in the clinic, this will be obtained in the clinic. In the event the visit is missed, or the patient cannot come to the clinic, the collection of samples at local facility is acceptable if the results can be made available to investigative site.				X		X		
Pharmacokinetic Sample Collection	Since atezolizumab needs to be given every 2 weeks in the clinic, this will be obtained in the clinic.	X	X	X	X	X			
Blood Sample for FLT3 and AXL	This is an exploratory endpoint. There are no alternative approaches for this assessment. If the 24 post-dose sample is not feasible, it is okay.	X							
Blood Sample for Immune Cell Immunophenotyping	In general biomarker samples are collected on atezolizumab treatment days and do not require a unique visit to the study site. These samples cannot be stored. If samples cannot be received by central lab then they should not be collected	X		X	X		X		
Blood Sample for Blast Cell Immunophenotyping	In general biomarker samples are collected on atezolizumab treatment days and do not require a unique visit to the study site. These samples cannot be stored. If samples cannot be received by central lab then they should not be collected	X		X	X		X		
PGx (whole blood and buccal swab)	This samples are collected on an atezolizumab treatment day. If the samples can be collected but the central lab cannot receive samples, samples can be stored at sites until shipping is accepted again	X							
Pregnancy Test for WOCBP	Since atezolizumab needs to be given every 2 weeks in the clinic, this will be obtained in the clinic. In the event the visit is missed, or the patient cannot come to the clinic, the collection of samples at local facility is acceptable if the results can be made available to investigative site.	X			X		X		

Treatment									
Gilteritinib Dosing at the Clinic	Patient will be taken off study and the patient can take commercially available gilteritinib off study or receive other alternative therapies for R/R AML albeit the options are limited and not very effective. Delivery from site to patient if the patient is just on gilteritinib monotherapy is also possible.	X	X	X	X	X			
Atezolizumab Dosing at the Clinic	All atezolizumab dose needs to be administered in the clinic at every 2 week intervals. The protocol allows for patients to continue treatment with gilteritinib alone if the patient had issues related to tolerability of other clinical considerations related to atezolizumab.	X		X	X	X			
Tissue Collection									
Bone Marrow Biopsy and/or Aspiration for disease assessment and MRD	Bone marrow assessment to be performed in the clinic. In the event this is not possible, bone marrow biopsy performed in a local facility is acceptable if results can be made available to investigative site.				X		X		
Diary									
Subject Diary for Gilteritinib	Diary can be shipped directly to the patient. Accountability can be performed during the telehealth visit.	X			X				

AE: adverse event; AML: acute myeloid leukemia; AXL: a receptor tyrosine kinase encoded by the AXL gene; C: cycle; D: day; ECG: electrocardiogram; ECOG: Eastern Cooperative Oncology Group; EOT: end of treatment; FLT3: FMS-like tyrosine kinase 3; MRD: minimal residual disease; PGx: pharmacogenomics; R/R: relapsed or refractory; SAE: serious adverse event; WOCBP: women of childbearing potential.

INVESTIGATIONAL PRODUCT SUPPLY

If any of the conditions outlined above in the Participants Procedures Assessment are met, one or all of the following mitigating strategies will be employed, as needed, to ensure continuity of study supply to the participants:

- **Increase stock of study drug on site to reduce number of shipments required, if site space will allow**
- **Use of locally available atezolizumab brands**
- **Direct-to-Participant shipments of study drug from the site to the participant's home (ASP2215 only)**

DATA COLLECTION REQUIREMENTS

Additional data may be collected in order to indicate how participation in the study may have been affected by a crisis and to accommodate data collection resulting from alternate measures implemented to manage the conduct of the study and participant safety.

- **Critical assessments for safety and efficacy based on study endpoints to be identified as missing or altered (performed virtually, at alternative locations, out of window, or other modifications) due to the crisis**

III. Nonsubstantial Amendment Rationale:

Rationale for Nonsubstantial Designation

All revisions made to the protocol are administrative in nature and do not impact the safety or scientific value of the clinical study.

